6.4. SAMPLE SIZE CALCULATION

A total number of 212 participants will be included. Based on prior studies on a PM+ intervention (Bryant et al., 2017; Rahman et al., 2016b), we aim to detect a small to medium effect size Delta (defined as the square root of the ratio of the variance of the tested effect to the comparison error variance) of 0.3 in the PM+ group at 2 months post-treatment based on the primary composite outcome PHQ-ADS (Kroenke et al., 2016; 2019). The PHQ-ADS is the combined sum score of depression and anxiety symptoms of the PHQ-9 and GAD-7, respectively and has shown good internal consistency ($\alpha = .88$ to $.92$) (Kroenke et al., 2016; 2019). A power calculation for an ANOVA repeated

measurement design with two time-periods to identify the effect of treatment at the last endpoint suggests a minimum sample size of $N=74$ per group (power=0.95, $\alpha=0.05$, two-sided, $\rho=0.9$). Taking into account 30% attrition, we aim to include a total number of 212 participants (106 in the stepped-care DWM/PM+ treatment group - with PFA and CAU - and 106 in the PFA and CAU comparison group).

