10.1 PRIMARY OUTCOME(S)

The statistical analysis of the RCT will estimate effectiveness of the stepped-care DWM/PM+ with PFA and CAU intervention compared to PFA and enhanced CAU alone, with PHQ-ADS score as the primary study outcome.

The primary outcome will be summarized using number of subjects (n), minimum and maximum; and means, standard deviations (SD) for normally distributed data, or medians and inter-quartile ranges for non-normally distributed data. To measure comparisons at baseline between the two treatment groups t -tests (continuous variables) or chi-squared test (categorical variables) will be conducted for normally distributed data; Mann-Whitney tests will be conducted for continuous non-normally distributed data.

Both intention-to-treat (ITT) analysis, including all randomized participants ($n=212$), and completers' (per protocol - PP) analysis will be carried out. The main conclusion of the trial will be based on the ITT analysis of the primary outcome. A secondary analysis of the primary outcome will also be presented using the PP population.

The statistical analysis will be masked, i.e. the trial statistician will be blinded to the treatment groups until the analysis has been completed. Moreover, the trial statistician will not be involved in determining participants' eligibility, in administering the intervention, in measuring the outcomes or in entering data.

To estimate the treatment effect, a linear mixed model will be employed for the primary endpoint analysis, which will have treatment as fixed effects, baseline measurement of primary endpoint as covariate, and subject as random effects. The mean difference between two treatment arms at each visit/time together with its 95% confidence interval will be derived from the mixed model. Covariate-adjusted mixed model of primary endpoint will also be performed by adding pre-specified covariates at baseline (gender, age, education, prior trauma, COVID-19 related events and stressor list) into the above model.

Missing data

Missing data will be treated as missing at random (MAR). No imputations of missing values will be made, as multilevel models can deal with missing data (Singer, Willett & Willett, 2003).

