10.2 SECONDARY OUTCOME(S)

Economic outcomes

Health economic analysis will be conducted to determine the difference in costs and outcomes in the intervention arm as compared to the care as usual group at each time-point. Primary analysis will be the total costs over the 2-month follow-up treatment period. Between-group comparison of mean costs will be completed using standard t-test with ordinary least squares regression used for adjusted analysis, with the validity of results confirmed using bootstrapping. Pseudonymised data will be sent to the London School of Economics and Political Science, partner in RESPOND under Work Package 3, for the health economics analysis of the CSRI.

Analysis of secondary outcomes with repeated measurements

Additionally, a linear mixed model as mentioned for the primary outcome analysis (PHQ-ADS) will be carried out for analyzing the following clinical outcomes measured at baseline, at 2 weeks after DWM, at 1 week and at 2 months after finishing PM+: posttraumatic stress reactions (PCL-5), depressive symptoms (PHQ-9), generalized anxiety (GAD-7), resilience (MIMIS) and quality of life (EQ-5D-5L).

Analysis of other secondary outcomes

Changes in caseness of the composite measure anxiety and depression will be calculated using the recommended cut-off of >20 for moderate severity on the PHQ-ADS questionnaire (Kroenke et al., 2016; Kroenke et al., 2019) and will be analyzed using a hierarchical logistic model with the same fixed and random effects as the hierarchical linear models above, from which odds ratio of having a depression together with 95% CI at each time point will be derived.

Corrections for multiple testing

Models will be tested on $\alpha = .05$; to deal with problems associated with multiple testing, for each time point T2-T4 the hypothesis that the experimental intervention has no effect on secondary outcome scores will be tested by performing the Seemingly Unrelated Regression equations model (Zellner, 1962), controlling for baseline values.

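### The reason given for not imputing covers only multilevel models, so the total-cost comparison and the seemingly unrelated regression tests become complete-case analyses at the planned 30% attrition

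*Protocol*

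**What the plan says.** Protocol 10.1, under Missing data, sets the assumption, "Missing data will be treated as missing at random (MAR"), and then the rule: "No imputations of missing values will be made, as multilevel models can deal with missing data". No other missing-data rule appears in the protocol.

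Most planned models fit that reason. The primary model and its covariate-adjusted version (10.1) are linear mixed models. PCL-5, PHQ-9, GAD-7, MIMIS and EQ-5D-5L get the same type of model (10.2), and PHQ-ADS caseness gets a hierarchical logistic model.

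Two analyses in 10.2 do not:

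- Economic outcomes: "Between-group comparison of mean costs will be completed using standard t-test with ordinary least squares regression used for adjusted analysis", with bootstrapping to confirm the results.
- Corrections for multiple testing: the hypothesis of no effect on the secondary outcomes at each of T2 to T4 "will be tested by performing the Seemingly Unrelated Regression equations model", controlling for baseline.

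On the expected loss, 6.4 states: "Taking into account 30% attrition, we aim to include a total number of 212 participants". Section 8.5 repeats the 30%.

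**The concern.** A likelihood-based mixed model keeps a person who has some follow-up visits and uses those visits to inform the missing ones. That is why missing at random is enough for it. A t-test or OLS on a cost total, and a regression system fitted separately at each visit, have no such mechanism. A person without the total, or without that visit, drops out of the analysis, and the scores seen at other visits are not used. Bootstrapping resamples the people who remain and brings nobody back.

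Two results are exposed. Cost-effectiveness is part of the primary objective (4.1), and 8.3 (Implementation indicators) plans an incremental cost per change in the primary outcome and in quality of life. Costs would come from completers and the PHQ-ADS effect from the ITT mixed model, so one ratio would join two different sets of people. The SUR test is the protocol's only stated answer to multiplicity among the secondary outcomes. It could disagree with the mixed models for the same outcomes because of dropout alone.

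**Working it through.** **1. The plan's own sample size (6.4).** Inputs: Delta = 0.3, "defined as the square root of the ratio of the variance of the tested effect to the comparison error variance"; two-sided alpha 0.05; power 0.95. Using an F test with 1 and N-2 degrees of freedom and noncentrality N x Delta²:

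- N = 146: power 0.9496.
- N = 148: noncentrality 148 x 0.09 = 13.32, power 0.952.

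The smallest even total is 148, or 74 per group. With 30% attrition, 74 / 0.70 = 105.7, so 106 per group and 212 in total. The stated figures reproduce.

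**2. Complete-case numbers at T4.** 212 x 0.70 = 148.4, about 74 per arm. Against full data, the standard error rises by √(106/74) = 1.20. The difference detectable in a t-test with 80% power is (1.960 + 0.842) x √(2/n):

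- n = 106 per arm: 0.38 SD.
- n = 74 per arm: 0.46 SD.

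Losses at T2 and T3 may be smaller; the protocol gives no figure for them.

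**3. Bias in a per-visit regression.** This is an illustrative simulation. All of its inputs are assumptions, except the 30% attrition and the value 0.9, which is the only correlation the protocol states (6.4, for PHQ-ADS).

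- Scores at T1 to T4 are multivariate normal with SD 1 and a true T4 effect of -0.30 SD.
- 30% are missing at T4. The log-odds of dropout are linear in the observed T3 score, so the data are missing at random.
- The complete-case estimate regresses T4 on arm and baseline. The comparator also uses T2 and T3, as a likelihood method does.
- Slopes are per SD of T3: 0.7 and 1.0 are odds ratios of 2.0 and 2.7, and -0.3 is an odds ratio of 0.74.
- The mixed correlations are 0.7, 0.6 and 0.5 of T2, T3 and T4 with baseline, 0.75 for T2-T3 and T3-T4, and 0.65 for T2-T4.

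Bias of the complete-case estimate in SD (a minus sign favours the intervention):

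| Dropout slope, treatment / control | All correlations 0.9 | All 0.7 | Mixed |
|---|---|---|---|
| Equal (0.7/0.7 or 1.0/1.0), 30% lost in each arm | 0.00 | 0.00 | 0.00 |
| 0.7 / 0 | -0.02 | -0.04 | -0.09 |
| 1.0 / 0 | -0.02 | -0.05 | -0.12 |
| 0.7 / -0.3 | -0.03 | -0.06 | -0.13 |

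If one dropout model with a common intercept applies to both arms, the bias is at most 0.02 SD, towards no effect. A deliberately extreme case, slopes of 1.0 and -1.0, gives -0.05, -0.12 and -0.24. The comparator that uses T2 and T3 stays within 0.003 SD of the truth in every case.

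**4. Scale.** The protocol expects a Cohen's d of 0.3 on the primary outcome (8.1.1). As a yardstick only, 0.02 / 0.30 = 7% and 0.13 / 0.30 = 43%. The simulation is for a continuous score. The documents give nothing from which to size the bias in costs.

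**The case against.** **The rule's reach is inferred.** The sentence stands under the primary outcome and its reason is about multilevel models. Section 10.2 never applies it to costs or SUR, and an SAP that is not shown may give a method. This stands in part. But the sentence is worded without limit, 10.2 takes its models from 10.1, and no other rule exists. A statistician working from the protocol would not impute.

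**Differential dropout is assumed.** This stands for the sizes. The direction is not far-fetched. Under 8.4, participants with suspected worsening are asked to withdraw, and helpers' calls are one route by which deterioration is noticed. The weekly calls take place in the treatment arm only, so worsening may be picked up more often there. That is an inference, not something the protocol says.

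**Stronger readings that the documents do not support:**

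- A reader might infer that the covariate-adjusted primary model also becomes complete-case at 30% attrition. It is a mixed model, and its covariates are measured before randomisation (8.2). It loses only people with a missing baseline item: 212 x 0.98 = 208, 212 x 0.95 = 201 or 212 x 0.90 = 191 remaining, at assumed rates of 2%, 5% or 10%.
- A reader might infer that the complete-case contrast is invalid whenever dropout is related to T2 or T3. With the same mechanism in both arms the bias is about zero.
- A reader might see 148 as a shortfall. It equals the planned evaluable number.
- A reader might assume that the cost total needs the CSRI at every visit. The protocol gives no recall window, so which visits enter is unknown.
- Dropping everyone with any missing secondary outcome is usual SUR software behaviour, not protocol text. A version that allows unequal numbers per equation would still ignore other visits.

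**Conclusion.** The point holds for two analyses: the total-cost t-test/OLS and the SUR tests at T2 to T4. The protocol bars imputation for a reason that does not apply to them, and as written they rest on completers, about 148 of 212 at T4. The matter is mainly one of possible bias and of departing from ITT; the number planned as evaluable is still reached.

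The bias is conditional. It needs dropout that depends on intermediate scores differently by arm. For the moderate slopes assumed above it lies between 0.02-0.03 SD (all correlations 0.9) and 0.09-0.13 SD (lower mixed correlations). It favours the intervention when poor scorers leave the treatment arm. The 0.9 in the protocol is for PHQ-ADS; nothing is stated for the other outcomes or for costs.

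The main conclusion of the trial, which rests on the ITT mixed model, is not affected. Nor are the mixed-model estimates for the secondary outcomes. The change should be made because cost-effectiveness is in the primary objective and SUR is the only multiplicity safeguard, but it does not threaten the primary result.

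**What to change.** - In 10.1, limit the no-imputation sentence to outcomes analysed by mixed models.
- In 10.2, for costs and QALYs, specify multiple imputation by arm, with observed costs, PHQ-ADS and EQ-5D-5L at T1 to T4 in the imputation model, combined with the planned bootstrap. State which CSRI assessments make up the cost total.
- Run the SUR joint test on the same imputed data, with the secondary outcomes included in the imputation, or replace it with a joint mixed model over T2 to T4.
- For the covariate-adjusted model, at most one sentence: sporadic missing baseline covariates are filled by simple imputation, so that no randomised participant is excluded.

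This costs rewording of two sections and modest extra programming, with no new data. The downside is reliance on an imputation model, whose variables should be fixed before the data are unblinded.

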10.2 SECONDARY OUTCOME(S)

Economic outcomes

Health economic analysis will be conducted to determine the difference in costs and outcomes in the intervention arm as compared to the care as usual group at each time-point. Primary analysis will be the total costs over the 2-month follow-up treatment period. Between-group comparison of mean costs will be completed using standard t-test with ordinary least squares regression used for adjusted analysis, with the validity of results confirmed using bootstrapping. Pseudonymised data will be sent to the London School of Economics and Political Science, partner in RESPOND under Work Package 3, for the health economics analysis of the CSRI.

Analysis of secondary outcomes with repeated measurements

Additionally, a linear mixed model as mentioned for the primary outcome analysis (PHQ-ADS) will be carried out for analyzing the following clinical outcomes measured at baseline, at 2 weeks after DWM, at 1 week and at 2 months after finishing PM+: posttraumatic stress reactions (PCL-5), depressive symptoms (PHQ-9), generalized anxiety (GAD-7), resilience (MIMIS) and quality of life (EQ-5D-5L).

Analysis of other secondary outcomes

Changes in caseness of the composite measure anxiety and depression will be calculated using the recommended cut-off of >20 for moderate severity on the PHQ-ADS questionnaire (Kroenke et al., 2016; Kroenke et al., 2019) and will be analyzed using a hierarchical logistic model with the same fixed and random effects as the hierarchical linear models above, from which odds ratio of having a depression together with 95% CI at each time point will be derived.

Corrections for multiple testing

Models will be tested on $\alpha = .05$; to deal with problems associated with multiple testing, for each time point T2-T4 the hypothesis that the experimental intervention has no effect on secondary outcome scores will be tested by performing the Seemingly Unrelated Regression equations model (Zellner, 1962), controlling for baseline values.

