| - Face-to-face or | PM+ tool | Screeener | x | | | x | x | | |
| - Self-administered | Step-by-step question | Screeener | x | | | x | | x | x |
| Mental, neurological or substance use disorders | PM+ tool | Screeener | x | | | | | | |
| Depression and Anxiety: | PHQ-ADS | Primary | | | | | | | |
| Subscale depression | PHQ-9 | Secondary | | x | | x | | x | x |
| Subscale anxiety | GAD-7 | Secondary | | x | | x | | x | x |
| Posttraumatic stress reactions | PCL-5 | Secondary | | x | | x | | x | x |
| Self-identified problems | PSYCHLOPS | Secondary | | x | | x | | x | x |
| Resilience | MIMIS | Secondary | | x | | x | | x | x |
| Resilience factors | PASSc | Secondary | | x | | x | | x | x |
| Quality of life | EQ-5D-5L | Secondary | | x | | x | | x | x |
| Impact on resource use/costs | CSRI | Secondary | | x | | x | | x | x |
| Socio-demographics | | Other | | x | | | | | |
| COVID-19 exposure | Questionnaire | Other | | x | | x | | x | x |
| Exposure to life events | BTQ | Other | | x | | | | x | |
| Treatment fidelity: | Metadata | Other | | | | x | | | |
| - DWM | | | | | | | | | |
| - PM+ | Audio records | Other | | | | | x | | |
| Satisfaction DWM | CSQ Interview | Other | | | | x | | | |
| Satisfaction PM+ | CSQ Interview | Other | | | | | | x | |

Screeners

Screening instruments

K10: psychological distress

Psychological distress will be measured using the Kessler-10 Psychological Distress Scale (Kessler et al., 2002). The K10 is a ten-item self-report questionnaire to screen broadly for psychological distress (e.g. anxiety and depression related distress) experienced in the past 30 days. Items are rated on a five-point Likert scale ranging from *none of the time* to *all of the time*. The sum of the ten items gives a total score ranging from 10 to 50. Higher scores represent higher levels of distress. The K10 has strong psychometric properties and has strong discriminatory power to distinguish DSM-IV cases from non-cases (Kessler et al., 2002). The K10 has been validated in various population samples and is a useful instrument in both primary care (Kessler et al., 2002) and general population samples (Furukawa, Kessler, Slade & Andrews, 2003; Kessler et al., 2005). Moreover, the K10 has been found to not have any substantial bias in regards to education level and gender, thus making it useful for research (Baillie, 2005). The K10 exists in various languages, among which are English and Italian.

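### The joint SUR test named as the multiplicity correction gives only weak, per-visit control and leaves the individual secondary outcomes unadjusted

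*Protocol*

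**What the plan says.** Protocol 10.2 has a paragraph headed as the correction for multiple testing. It sets the level ("Models will be tested on $\alpha = .05"), states the purpose ("to deal with problems associated with multiple testing, for each time point T2-T4 the hypothesis that the experimental intervention has no effect"), and names the method: the no-effect hypothesis for the secondary scores "will be tested by performing the Seemingly Unrelated Regression equations model", controlling for baseline. That makes one joint test at each of T2, T3 and T4.

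Earlier in the same section, five clinical secondary outcomes (PCL-5, PHQ-9, GAD-7, MIMIS and EQ-5D-5L) are each given their own analysis: "a linear mixed model as mentioned for the primary outcome analysis (PHQ-ADS) will be carried out". Under 10.1 that model yields an arm difference with a 95% confidence interval at every visit.

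The text does not divide alpha over the three visits. It gives no rule leading from the joint test to a single outcome, and it does not label the single-outcome results as unadjusted or exploratory. Section 10.1 rests the trial's main conclusion on the ITT analysis of the primary outcome.

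**The concern.** The protocol chooses to correct the secondary outcomes and fixes the means of doing so. The question is therefore whether that method does the job, and not whether secondary outcomes need adjustment at all.

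A joint SUR test answers one question: is there an effect on at least one outcome at this visit? It does not say which outcome. Repeating it at three visits at the full 5% leaves the error across visits unprotected.

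The statements most likely to be made are about single outcomes: an effect on PTSD symptoms, on resilience, on quality of life. These come from the mixed models, to which the correction is not attached. A reader who sees a heading promising a correction may take those statements as protected when they are not.

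**Working it through.** **Inputs from the Protocol.** Alpha .05 per model, three visits and five outcomes (10.2). One contrast per outcome and visit (10.1), so 5 × 3 = 15 contrasts. PHQ-ADS is the sum of PHQ-9 and GAD-7 (8.3, primary outcome measure).

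**Assumptions, not in the Protocol.** Test statistics are jointly normal with exchangeable correlation, 0-0.7 between outcomes and 0-0.9 between visits. A truly responding outcome has mean z = 3.5. The SUR test is taken as a large-sample Wald chi-square test on 5 df. Each simulation used 200,000 sets.

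**Step 1. The stated level, one visit.** Simulated rejection under the global null is 0.049-0.051. The stated 5% is reproduced: at a single visit the joint test does what it should across the five outcomes.

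**Step 2. Three joint tests.** The upper bound is 3 × 0.05 = 0.15. With independent visits, 1 − 0.95³ = 0.143. With correlated visits, by simulation:

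| Between-visit correlation | Any false joint rejection, each at .05 | Each at .05/3 = .0167 |
|---|---|---|
| 0 | 14% | 4.9% |
| 0.5 | 13% | 4.6% |
| 0.7 | 11% | 4.1% |
| 0.9 | 8.7% | 3.1% |

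**Step 3. Single outcomes without adjustment, global null.** Five outcomes at one visit: 1 − 0.95⁵ = 0.226 if independent, and 15-21% at outcome correlation 0.7-0.3. All 15 contrasts: 1 − 0.95¹⁵ = 0.537 if independent, and 23-50% at outcome correlation 0.3-0.7 and visit correlation 0-0.9.

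**Step 4. The most favourable reading: SUR as a gate.** Suppose single outcomes are claimed at a visit only when its joint test rejects. Under the global null this holds 3-5% per visit. Once an outcome truly responds, the gate is nearly always open and no longer protects the others. At T4:

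| Outcomes truly responding | Outcome correlation | Gate opens | False claim among the rest, gate only | Same, Holm over five |
|---|---|---|---|---|
| 1 | 0.4 | 92% | 16% | 4% |
| 1 | 0.7 | almost 100% | 13% | 3% |
| 2 | 0.4 | 99% | 13% | 4% |
| 2 | 0.7 | 100% | 11% | 3% |

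The two-outcome rows represent PHQ-9 and GAD-7 both responding. A true effect on their sum requires an effect on at least one of them, so whenever the primary effect is real the T4 joint null is already false. The gate then says nothing about PTSD symptoms, resilience or quality of life.

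**The case against.** The best defence has three parts.

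First, the joint test is a real correction. At each visit it replaces five tests with one at 5%, and the Protocol only says it will deal with the problems of multiple testing; it does not promise familywise control over visits or single outcomes. This stands. A reader might infer that the Protocol has no multiplicity control at all; step 1 shows otherwise.

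Second, the gating order, the visit of interest and the labelling of secondary p-values often go into a statistical analysis plan, which is not at hand. This stands in part. Such a plan could add Holm and settle the matter. But 10.2 already fixes the method and the level under a heading that calls it the correction. Followed as written it does not cover visits or single outcomes, and adding a gate alone leaves the 11-16% of step 4.

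Third, the correlations and the mean z of 3.5 are chosen values. This is true, and the results are given as ranges for that reason. The direction does not depend on them: three unsplit tests exceed 5% unless the visits are almost perfectly correlated, and an open gate gives no protection.

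**Conclusion.** The correction in 10.2 is weak, applies within a visit only, and does not support claims on individual secondary outcomes. Under the global null, any false joint rejection over T2-T4 has a probability of about 9-13% at assumed visit correlation 0.5-0.9, or 14% if visits are independent. With one or two true T4 effects (assumed mean z 3.5, outcome correlation 0.4-0.7), false claims on the remaining outcomes run at 11-16% even if SUR is treated as a gate, against 3-4% with Holm.

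Three further inferences are not supported:
- **That the main conclusion is at risk.** It rests on the primary outcome alone, which lies outside this family.
- **That the joint test must drop participants with incomplete outcomes because 10.1 rules out imputation.** The Protocol does not say how SUR will be fitted, and likelihood fitting with missing responses is possible.
- **That the labelling of PSYCHLOPS and PASSc as secondary in Table 1 shows the test to fail.** That is a separate matter of outcome lists. Section 8.1.2 already lists the same five clinical outcomes that 10.2 models.

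**What to change.** In Protocol 10.2, preferably:
- name T4 as the visit for secondary inference;
- apply Holm at 5% to the five listed T4 mixed-model contrasts;
- report T2 and T3 contrasts with unadjusted confidence intervals, labelled exploratory;
- if wanted, keep a single T4 SUR test at .05 as a global test. Holm does not need it.

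Alternatively, keep SUR at all three visits at .05/3 = .0167 each, and state that individual-outcome results are unadjusted and exploratory.

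Either version is a few sentences and needs no new model. The price of Holm is a stricter first threshold, 0.05/5 = 0.01. For an outcome with mean z 3.5, power at .05 is Φ(3.5 − 1.960) = Φ(1.540) ≈ 0.94, and at .01 it is Φ(3.5 − 2.576) = Φ(0.924) ≈ 0.82. The second figure applies when no other outcome has been rejected first. The first option also gives up confirmatory statements at T2, the assessment after step 1. The alternative keeps a joint test there but allows no protected claim on any single outcome.
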